3.1. Inclusion Criteria

1. Age 18-65
2. Less than Bachelor's degree
3. Smoke >4 cigarettes/day for at least a year
4. Willing to smoke one flavor of cigarette during the trial (menthol or non-menthol)
5. Read and write in English
6. Able to understand and consent to study procedures
7. Plan to live in the local area for the next 8 months
8. Women not pregnant or nursing and taking steps to avoid pregnancy
9. No quit attempt in the past month and not planning to quit in the next 6 months (ensuring stability of smoking).
10. Ability to consistently receive phone calls over the next 8 months
11. Participants who become prisoners or otherwise subject to correctional supervision through probation, parole, home confinement, electronic monitoring, work release or other monitored, non-custodial supervision after signing the consent form.

Notes Related to Prisoner Participation

- The prisoner participant must be permitted by their probation/parole officer, court or other supervising authority to go to the research office visits, and the devices need to be programmed to reflect that additional time/place of travel. These issues will be resolved by the prisoner and their supervising authority on a case-by-case basis.

Rationale to include prisoners: Potential benefit of the subject (intent and reasonable probability of improving the health or well-being of the subject)

3.2. Exclusion Criteria

1. College graduate
2. Currently pregnant or nursing
3. Systolic blood pressure greater than or equal to 160
4. Unstable or significant medical condition such as COPD or kidney failure that is likely to affect biomarker data
5. Use of non-cigarette nicotine delivery product in the past week (included cigars, pipes, chew, snus, hookah, e-cig, and marijuana)

6. Currently reducing or planning to reduce cigarette consumption in the next month
7. Use of smoking cessation medicine in the past month
8. History of difficulties providing blood samples; fainting, poor veins, anxiety, etc.
9. Regular use (more than weekly) of illegal drugs or prescription drugs used for non-medical purposes in the past 3 months or inpatient treatment for these in the past 6 months.
10. Uncontrolled serious psychotic illness (includes schizophrenia, bipolar disorder, eating disorder, and dementia) or inpatient treatment for a mental health condition in the last 6 months
11. Alcohol abuse that would hinder the participant's ability to participate
12. Significant medical condition i.e. stroke, MI, cancer in the last month
13. Other members of the household are currently participating in a trial related to reduced nicotine cigarettes
14. Taking an out of town trip or vacation in the next 8 months that will last 3 weeks or more or has major surgery planned in the next 8 months
15. Any other condition or situation that would, in the investigator's opinion, make it unlikely that the participant could comply with the study protocol
16. Participants who are prisoners at time of enrollment
17. Participants who become custodial inmates at any correctional facility after enrollment in the research.

3.3. Early Withdrawal of Subjects

3.3.1. Criteria for removal from study

Participant withdrawal prior to randomization (Baseline Phase I and II)

These two phases are designed to identify participants who are not able or willing to comply with the full study protocol. During Baseline I, participants will smoke their own usual brand of cigarettes for 1 week. At Baseline II, all participants will be asked to smoke research cigarettes with a normal amount of nicotine. Participants who are removed during these two phases will be replaced prior to randomization until a total of 200 participants have been randomized (same for George Washington University).

Those who are not compliant with the study protocol prior to randomization for any of the following reasons will be withdrawn from the study **either during Baseline Phase I or Phase II:**

1. **Participant reports using any non-cigarette nicotine products at more than one visit.** Includes cigars, pipes, snuff, chew, hookah, electronic cigarette, marijuana, or any other illegal smoked substance, or any other nicotine containing product.

Those who are not compliant with the study protocol prior to randomization for any of the following reasons will be withdrawn from the study **during Phase II only:**

1. **Participant consumes more than 10% of cigarettes consumed are non-research cigarettes** in the 6 days prior to visit 3 only (Average cigarettes from day 15-20, e.g. 4 or more out of 30 cigarettes in 6 days for a 5 CPD smoker; 18 or more out of 180 cigarettes in 6 days for a 30 CPD smoker).
2. **Participant has reduced their cigarette consumption by more than 50% compared to baseline cigarettes per day** (when cigarettes per day are averaged over days 15-20) **because of non-compliance. This does not include situations of illness or other circumstances that would interfere with the participants' normal smoking behavior.**

Participant withdrawal at any point during the study if any of the following occurs:

1. **New pregnancy:** Participants who report a new pregnancy at any point during the study will be withdrawn or confirmed by urinary pregnancy test.
2. **Cardiovascular disease (CVD) event:** Typically includes MI (heart attack), PTCA (angioplasty/stenting), bypass surgery, stroke, peripheral vascular disease (arterial blockages in arms or legs leading to procedure or surgery). Less common CVD problems would be new cardiac arrhythmias (e.g., new atrial fibrillation) or new valvular disease (e.g., mitral or aortic regurgitation).
3. **DVT/PE (deep vein thrombosis/pulmonary embolism, i.e., blood clots in the venous system):**
4. **Participant choice:** Participants may choose to remove themselves from the study by informing the research team in writing or verbally at any point during the study.

The following will be monitored and can lead to the participant being withdrawn at any point by the PI:

1. **Expired breath carbon monoxide increase:** If the average of two consecutive CO measurements in the same visit is
 - i. CO is greater than 50 ppm if CO at baseline visit 1 is <20 ppm.
 - ii. CO is greater than 60 ppm if CO at baseline visit is 1 20 – 34 ppm.
 - iii. CO is greater than 70 ppm if CO at baseline visit is 1 35 – 49 ppm.
 - iv. CO is greater than 80 ppm if CO at baseline visit is 1 50 – 60 ppm.
 - v. CO is greater than 90 ppm if CO at baseline visit is 1 61 – 70 ppm.If the average of the two readings is still out of range after testing twice, an AE will be documented and the participant will be monitored by the medical professional.
2. **Cigarette per day increase:** The average CPD increases by more than 100% from the average CPD at the baseline assessment visit.
3. **Increase Systolic Blood Pressure** over >160 mmHg
4. **Increased substance abuse** in which the participant is behaving inappropriately at visits or demonstrates an inability to continue with the study.
5. **Any hospitalization or debilitation** in which participation in the study could be detrimental to the recovery process. This will be self-reported by the participant and will be reviewed by the site PI and medical professional to determine whether continued participation in the study is appropriate.
6. **Any Missed visits** where the participant would have received new research cigarettes. Of concern is what type of cigarettes (research or own brand) the participant has been smoking if they did not attend a visit where they would have received research cigarettes. Participants will be reviewed and considered for withdrawal on a case by case basis.
7. **Any situation where participant is not able to smoke research cigarettes for a period of more than 2 weeks**
8. **Participant behavior:** If a participant is behaving in an inappropriate or threatening manner, demonstrates an inability to continue with the study, admits to lying about eligibility criteria, is participating in other smoking research studies that could affect the primary outcome measures, etc., then the PI can withdraw him/her from the study at the PI's discretion.
9. **Significant baseline smoking rate increase:** A participant may be withdrawn from the study if they meet **BOTH** of the following criteria (only if receiving research cigarettes):
 - a. **Cigarette per day increase:** The average CPD increases by more than 100% from the average CPD at the baseline assessment visit

b. **Expired breath carbon monoxide increase:** If the average of two consecutive CO measurements in the same visit is:

- i. CO is greater than 50 ppm if CO at baseline visit 1 is <20 ppm.
- ii. CO is greater than 60 ppm if CO at baseline visit 1 is 20 – 34 ppm.
- iii. CO is greater than 70 ppm if CO at baseline visit 1 is 35 – 49 ppm.
- iv. CO is greater than 80 ppm if CO at baseline visit 1 is 50 – 60 ppm.
- v. CO is greater than 90 ppm if CO at baseline visit 1 is 61 – 70 ppm.

3.3.2. Follow-up for withdrawn subjects

Subjects are withdrawn if they provide a verbal or written request to be removed from the study at any time after the initial consent. All data collected up to the withdrawal date will be included in the analysis of the data with Intent to Treat statistical rules. If a subject consents but is not randomized, or is consented but does not complete the baseline evaluation and assessments, the subject will be replaced. Subjects who withdraw themselves will be asked to complete a questionnaire (named End of Trial Questionnaire in Appendix of Coordinator entered Surveys) regarding the reasons for dropping out. Subjects that were selected to use a topography machine (see below) will be asked to use the machine for 1 additional day.

4. Recruitment Methods

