1.1. Study Objectives

Specific Aims

1. Determine the effect of progressive nicotine content reduction on nicotine and its metabolites and other biomarkers of smoking exposure.
 - a. Determine the effects of RNC (reduced nicotine content) cigarettes in both black and white smokers of lower SES (socioeconomic status) over an 18 week trial period. Subjects will be randomized to either, (i) gradual reduction in reduced nicotine content cigarettes, or (ii) cigarettes containing the nicotine content of their usual brand. It is expected that the gradual reduction of nicotine from progressively lowering nicotine exposure will lead to lower levels of blood nicotine metabolites and nicotine-derived 4-(methylnitrosamino)-1-(3-pyridyl)-1-butanol)(NNAL), while not affecting cigarettes smoked per.
 - b. Determine the modifying effect of menthol on progressive nicotine content reduction and biomarkers. It is expected that menthol will not modify the effect of progressive RNC cigarettes on the above biomarkers.
2. Determine the predictors of participant drop-out/relapse. We hypothesize that compensatory smoking behavior as measured by smoking topography and expired carbon monoxide (CO), a higher baseline nicotine dependence behavioral score, will be associated with dropout/ relapse.
3. Determine if a gradual reduction in RNC cigarettes vs. same nicotine content is associated with a reduction in stress. Psychological stress and nicotine stimulate the production of cortisol, a biomarker of stress pathways. It is expected that nicotine reduction will lead to initially higher levels

of psychological stress and cortisol associated with withdrawal but lowered levels of psychological stress/cortisol with long-term nicotine reduction.

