9.1. Sample size determination

The primary sample size calculation for this project will be based on hypothesis 1a and the main outcome variable is plasma cotinine concentration (measured as ng/ml). The mean value of this continuous variable will be compared between the control group and the experimental group. For plausible effect size and variation, we use results of Benowitz et al [4], where the mean (SD) of plasma cotinine concentration are 240 (120) for the control group and 113 (116) for the experimental group at the 21st week follow-up visit (end of randomization phase for trial). It is expected that the cotinine level in the experimental group is reduced gradually after the randomization and the mean difference of the cotinine level between these two groups at the beginning of the trial for our study will be smaller than the value of 127 ng/ml in Benowitz et al [4]. With a sample size of 70 participants per group, we are able to detect the difference in plasma cotinine concentration level between the two groups as small as 58 ng/ml with at least 80% power (and 68 ng/ml with at least 90% power). In this project we plan to study the mean change of plasma cotinine concentration separately for black and white populations. A total sample size of 280 (70 per group * 2 groups * 2 races) is then needed for this project. We plan to recruit a total of 400 participants for this project by allowing a 30% drop-out rate. The alpha level used for the power analysis is 0.05. Another biomarker of interest is the Glutathione (GSH, measured in μ mol/ml). Within each study population (black or white), a sample size of 70 per

group will enable us to detect a mean difference of GSH of 0.23 with at least 90% power. The common standard deviation is assumed to be 0.40 based on [name] et al (2004). For testing the menthol-by-group interaction effects, our proposed sample size will give us at least 80% power to detect a mean difference of plasma cotinine concentration of 72 ng/ml in the pair-wise comparison of among the group-by-menthol combination (4 levels, alpha is adjusted to 0.0083 by Bonferroni method).

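### The biomarker analysis is labelled intent to treat, but data end at withdrawal and no missing-data assumption or sensitivity analysis is stated, with 30% drop-out expected

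*Combined protocol and SAP*

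**What the plan says.** Section 3.3.2 describes withdrawal at the participant's request ("Subjects are withdrawn if they provide a verbal or written request to be removed from the study at any time after the initial consent") and then sets the analysis rule: "All data collected up to the withdrawal date will be included in the analysis of the data with Intent to Treat statistical rules". What follows withdrawal is limited: "Subjects who withdraw themselves will be asked to complete a questionnaire" on the reasons for leaving, and one further day with the device for those in the topography subset. No cotinine, NNAL or other biosample is scheduled.

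Section 3.3.1 also lets the PI withdraw randomised participants at discretion. The grounds include a large rise in expired CO, more than a doubling of cigarettes per day, a missed visit at which cigarettes would have been supplied, and more than two weeks without being able to smoke research cigarettes.

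Section 9.2 fits a linear mixed model for repeated measures with baseline as a covariate. It gives no estimand, no missing-data assumption and no sensitivity analysis. In Section 9.1, "the main outcome variable is plasma cotinine concentration (measured as ng/ml"), and "We plan to recruit a total of 400 participants for this project by allowing a 30% drop-out rate". Aim 2 in Section 1.1 hypothesises that compensatory smoking, expired CO and baseline dependence "will be associated with dropout/ relapse".

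**The concern.** An intention-to-treat effect compares the arms as randomised, whatever participants later smoke. The planned data cannot deliver this directly for biomarkers, because measurement stops when a participant leaves. A mixed model fitted to the remaining data fills the gap implicitly: each drop-out's later mean is taken to follow those still observed in the same arm, given that person's earlier values.

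That assumption is open to doubt here. Some PI withdrawal grounds are themselves signs of leaving the product or of compensating, and the protocol expects drop-out to go with compensation and CO. A participant who leaves the taper receives no more reduced-nicotine cigarettes. If that person resumes usual smoking, exposure rises again, while the model continues along the taper. Section 2.3 presents the trial as evidence needed before a national policy is fully endorsed, so a reader would take the label at face value.

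**Working it through.** **Inputs.** From Section 9.1: means (SD) "240 (120) for the control group and 113 (116) for the experimental group at the 21st week follow-up visit", a difference of 127 ng/ml; 70 per group; alpha 0.05 (taken as two-sided); 30% drop-out. Allocation is 1:1 (Section 7.4.3).

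**1. The plan's own figures.** Section 9.1 claims to detect a difference "as small as 58 ng/ml with at least 80% power (and 68 ng/ml with at least 90% power").
- Pooled SD = √[(120² + 116²)/2] = 118.0.
- With 70 per group, power is 82.8% for 58 ng/ml and 92.6% for 68 ng/ml (normal approximation; 82.3% and 92.3% with the t distribution).
- 280/(1 − 0.30) = 400.

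All reproduce.

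**2. Effect in all randomised.** Let d be the drop-out proportion, D the end-of-phase difference among those who remain, and D* the difference among drop-outs:

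E = (1 − d) × D + d × D*

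The documents do not give D*. Taking D = 127 is also an assumption. With d = 0.30, (1 − d) × D = 0.70 × 127 = 88.9.

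| Assumption about drop-outs | d × D* | E (ng/ml) |
|---|---|---|
| All return to 240 | 0 | 88.9 |
| Keep half the effect | 0.30 × 63.5 = 19.05 | 108.0 |
| Keep the whole effect | 0.30 × 127 = 38.1 | 127.0 |
| 25% of taper drop-outs quit | 72 × 0.25 = 18 | 106.9 |
| 50% of taper drop-outs quit | 72 × 0.50 = 36 | 124.9 |
| All taper drop-outs quit | 72 | 160.9 |

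In the quitting rows, a share q of taper drop-outs has cotinine near 0. The rest, and all control drop-outs, are at 240, so D* = 240 − (1 − q) × 240 = 240q and d × D* = 72q. There is no bias when 72q = 127 − 88.9 = 38.1, that is q = 38.1/72 = 0.53. Above that share the planned analysis understates the effect.

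Under full return, 127/88.9 = 1.43. Varying drop-out from 10% to 50% under full return gives E from 0.90 × 127 = 114.3 to 0.50 × 127 = 63.5.

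**3. What the mixed model targets.** A repeated-measures mixed model was simulated with 3,000 per arm, a random intercept, a baseline covariate, an assumed correlation of 0.7 and an assumed effect profile ending at 127. Drop-outs were set to return to usual cotinine.

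| Drop-out pattern | Mixed model | All randomised | Ratio |
|---|---|---|---|
| About 30%, at random | 128.7 | 90.2 | 1.43 |
| About 30%, depending on baseline cotinine | 127.2 | 87.3 | 1.46 |
| About 40% taper, 18% control | 122.8 | 73.3 | 1.68 |

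The gap is present even when drop-out is completely random. It comes from what is being estimated, not only from who leaves.

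**4. Detection.** With SD 118.0 and 70 per group, power for 88.9 ng/ml is above 99%. If the difference among those who remain were only 58, full return would leave 0.70 × 58 = 40.6 ng/ml, with 53% power at 70 per group and 68% at 100 per group (400/4).

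**The case against.** The strongest objection concerns direction. A reader might infer that the planned analysis overstates the effect. The documents do not support that as a fact, because they say nothing about what withdrawn participants smoke. Quitting is conceivable: Section 2.2 cites a study in which the lowest-nicotine cigarette led to more cessation than the intermediate one. Someone who had quit could also meet the two-week ground for PI withdrawal. Other grounds, such as pregnancy, a cardiovascular event or hospitalisation, need not reflect intolerance of the product. Against this, Section 3.1 requires no plan to quit within six months, and the protocol pairs drop-out with relapse. Return to usual smoking is therefore plausible, but it remains an assumption.

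A reader might also infer that the model gives the effect of staying on research cigarettes. It does not. After randomisation, withdrawal for being off product is discretionary, so participants who smoke other cigarettes but stay in the study keep contributing data.

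Nor are drop-outs left out. Their data up to withdrawal are kept, drop-out is part of the listed primary endpoint (Section 1.2.1), and Section 9.2 analyses time to drop-out. Drop-out that depends on measured variables is not by itself non-ignorable.

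Two further points stand. Section 3.3.2 opens with withdrawal on request, where later samples may be unobtainable, so the gap is clearest for PI-withdrawn participants. And under a national standard, return to a full-nicotine brand might not be possible, so which effect matters for policy is open to argument. Neither point supplies the missing assumption or sensitivity analysis.

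**Conclusion.** The concern stands in conditional form. The label does not match the planned biomarker analysis, which carries drop-outs along the path of those who remain. It would overstate the cotinine reduction in all randomised if drop-outs resume usual smoking. The extreme case considered, in which all 30% return to 240, gives 89 instead of 127 ng/ml. The gap is smaller if part of the effect persists, disappears at about 53% quitting among taper drop-outs, and reverses beyond that.

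These figures rest on another trial's means as quoted in Section 9.1, which does not say whether they describe completers or all participants. They cover cotinine only; the size for NNAL is not quantified. At these values an effect would still be detected, so the issue is how large it is and to whom it applies. The time-to-drop-out analysis is not affected.

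**What to change.** In Sections 3.3.2 and 9.2, state that the mixed model uses all randomised participants' data up to withdrawal under a missing-at-random assumption, and do not present it on its own as the intention-to-treat effect. Calling it the effect while on research cigarettes would be equally inaccurate.

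Pre-specify beside it a sensitivity analysis that multiply imputes post-withdrawal cotinine, NNAL and CO in both arms from each participant's own-brand value at Visit 2 (Section 7.2.2). Visit 3 is unsuitable as the reference because participants are by then smoking research cigarettes. Add a tipping-point range for drop-outs that runs from full return to usual exposure through to quitting, and report where the conclusion would change.

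The cost is SAP wording and one extra analysis, with no new visits. Section 7.2.2 says some biomarkers are assayed only in subgroups, so the SAP should confirm which Visit 2 values will exist. The stated effect may become less favourable.

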4.2. Recruitment process

This will be a randomized trial of cigarette smokers (n=400 with an expected dropout rate of 30% for a total of 280 smokers) recruited at two sites: Pennsylvania State University (n=200) and George Washington University (n=200). Recruitment materials will direct cigarette smokers to contact the study center by telephone or visit the Penn State TCORS website to complete the basic eligibility screener also called the Call routing screener- IRB protocol STUDY00002213). Once they complete this screener and they are eligible for one of our studies, they will be forwarded to the appropriate study coordinator for further screening.

4.3. Recruitment materials

All our general recruitment materials have been included under the IRB protocol STUDY00002213. They include flyers (with the header “Do you smoke” and the study center’s number listed below), radio advertisement script, and a letter to past participants.

In the HIV clinic, a study flyer will be posted and handed to potential participants that gives them information on the study (uploaded in Recruitment materials named Recruitment Letter to Clinic Participants).

4.4. Eligibility/screening of subjects

The Penn State Tobacco Center of Regulatory Science grant includes several projects that are recruiting smokers with similar, but not identical characteristics. In order to be efficient with recruitment and avoid confusion in the community, we will advertise one single study website and phone number where potential participants can go to obtain information on studies being conducted by TCORS primary investigators. Participants who are interested in the studies will complete the following screening process:

1. **Call Routing Screener- IRB protocol STUDY00002213 (either over the phone or on TCORS website):** This questionnaire is designed to identify the most common characteristics needed to participate any of the TCORS studies. An algorithm will be set up in REDCap that will deem them eligible for the appropriate study based off of their answers and inform the appropriate study coordinator from each project when a participant has completed the screener. They will leave information to be contacted by a study coordinator.
2. **Project Screener 1:** Once a participant has passed the Call Routing Screener, the appropriate study coordinator will conduct a second screening over the phone which will be more specific to their study. If the participant passes the second screener then a study visit (Screening /Assessment Visit 1) will be scheduled at PSH Clinical Research Center. Participants will verbally consent to their information being retained and being contacted for future studies. A full script and screening questions for this study are in the “Consent Forms and Recruitment Materials” section of the IRB application.
3. **Project Screener 2:** The participant will go through this last screener at their Screening /Assessment Visit 1 at the PSH Clinical Research Center. This screener will also have a review of the first and second screener to make sure nothing has changed since the coordinator last spoke with the participant. A full script and screening questions for this study are in the “Consent Forms and Recruitment Materials” section of the IRB application.

5. Consent Process and Documentation

